7.3 Intervention protocol

7.3.1. Initiation

The intervention will begin at the point when the preterm infant, who is receiving sufficient feeding via gavage (≥ 120 ml/kg/d), has reached a postmenstrual age (PMA) of at least 28 weeks and has been at least 48 hours since the removal of nasal continuous positive airway pressure (CPAP) therapy.

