[Protocol for Clinical Trial]

The effects of direct swallowing training and oral sensorimotor stimulation in preterm infants

2015.07

NCT02508571

Table of Contents

1. Title of the Clinical Trial	5
2. Name and Address of the Clinical Trial Institution	5
3. Study Period	5
4. Objectives of the Study	5
5. Study Design	5
6. Study Participants	5
7. Study procedures	7
8. Study evaluation	12
9. Dropout	15
10. References	16

[Clinical Trial Overview]

Clinical Trial Title	The effects of direct swallowing training and oral sensorimotor stimulation in preterm infants
Objective of the Clinical Trial	This study aims to evaluate whether the application of direct swallowing training (DST) and oral sensorimotor stimulation (OSMS) in preterm infants preparing for the transition from tube feeding to oral feeding shortens the time required for complete oral feeding and improves oral feeding skills. Additionally, the study will assess the long-term impact of oral feeding

Protocol_DST and OSMS_oral feeding performance

	interventions in the neonatal intensive care unit (NICU) on developmental outcomes and dietary habits.
Phase of the Clinical Trial	Prospective, blind, controlled, randomized trial
Clinical Trial Institution	Seoul National University Hospital
Principal Investigator	[name], Department of Pediatrics, Seoul National University College of Medicine
Study Design	single-center, prospective, open-label, controlled, randomized study
Study participants	
 -Gestational age at birth < 32+0 weeks -Eligible for respiratory support using heated humidified high-flow nasal cannula (HHFN) or equivalent, within 33+0 weeks -Infants who have been progressing with tube feeding at a volume of 120 ml/kg/day or more -Informed consent obtained from parents or legal guardians
Number of participants	189
Study methodology	
In this study, preterm infants who are receiving adequate tube feeding and have been discontinued from continuous positive airway pressure (CPAP) for at least 48 hours will be divided into three groups:
 
 - Control Group -DST Group (Direct Swallowing Training) -DST + OSMS Group (Direct Swallowing Training + Oral Sensorimotor Stimulation) 
Each group will receive its respective intervention.

Study period	From IRB approval date in 2015 to December 30, 2025.

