6.4 Inclusion and Exclusion criteria for enrolment

6.4.1. Inclusion criteria

- (1) Preterm infants with a gestational age of less than 32+0 weeks.
- (2) Infants currently receiving sufficient tube feeding (at least 120 ml/kg/day).
- (3) Infants who can be treated with heated, humidified high-flow nasal cannula (HFNC) within 33+0 weeks.
- (4) Infants who only have feeding-related issues remaining, with no need for special medical treatment.
- (5) Infants whose parents voluntarily sign the informed consent form for participation in the study.

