7.2 Randomization

In this study, eligible participants who meet all the inclusion criteria will be randomly assigned in a

Protocol_DST and OSMS_oral feeding performance

1:1:1 ratio to the control group, the DST group, or the DST + OSMS group. However, randomization will be stratified by gestational age and sex.

The randomization will be done using a block randomization method with block sizes of 3 and 6, generated through SAS 9.2. The randomization process will be managed via the MRCC website (<http://mrcc.snu.ac.kr>) using web-based randomization.

The detailed randomization procedure is as follows:

- Study coordinators will be provided with an ID and password for randomization.
- The study coordinators will log in to the MRCC website (<http://mrcc.snu.ac.kr>) and access the randomization screen.
- The study coordinator will enter the participant's basic information, test results, inclusion/exclusion criteria, and other relevant data, and click the confirmation button.
- If the participant is eligible, a randomization number will appear on the screen.
- The randomization screen will be printed, and one copy will be kept for records.
- The study coordinator will use the assigned randomization number to prescribe the corresponding intervention.

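### The plan gives two randomisation points: sections 6.4 and 7.2 omit start conditions set in section 7.3.1, and section 8.4.1 drops any randomised infant who never starts

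*Combined protocol and SAP*

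**What the plan says.** The overview (study methodology row) describes infants who "have been discontinued from continuous positive airway pressure (CPAP) for at least 48 hours will be divided into three groups". On that wording, allocation comes after CPAP removal.

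Section 7.2 says that "eligible participants who meet all the inclusion criteria will be randomly assigned in a" 1:1:1 ratio. It names no time point. The coordinator enters the infant's data on the web form, and a number appears if the infant is eligible.

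Eligibility is set in section 6.4. The respiratory criterion is "Infants who can be treated with heated, humidified high-flow nasal cannula (HFNC) within 33+0 weeks". Criterion (4) reads "Infants who only have feeding-related issues remaining, with no need for special medical treatment". Neither these nor the other inclusion and exclusion criteria state a CPAP-free interval or a minimum PMA. Section 7.1 (screening) adds no further check.

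Section 7.3.1 then sets conditions for starting the intervention: sufficient gavage feeding, an infant who "has reached a postmenstrual age (PMA) of at least 28 weeks", and one who "has been at least 48 hours since the removal of nasal continuous positive airway pressure (CPAP) therapy".

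Section 8.4.1 limits the ITT set to patients with one or more therapy sessions and one or more outcome assessments. The FAS (primary) and PP sets are drawn from that ITT set.

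**The concern.** If the number can be released before the infant is allowed to start, there is a wait between allocation and the first session, and failing to start becomes an event after randomisation. Because section 8.4.1 makes a first session a condition of membership in every analysis set, an infant who is randomised and does not start is removed from all planned comparisons. Such infants are likely to be those with slower respiratory recovery, so their loss is unlikely to be random with respect to feeding progress.

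The handling may also differ between arms. The screen procedure (numbered 10.4.3.3) gives controls a 15-minute period without intervention, and section 8.4.1 does not say what counts as a therapy session for them.

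At stake is the comparison of groups as randomised and, to a smaller degree, power.

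**Working it through.** **1. The conditions side by side**

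| Condition | Overview, methodology row | Section 6.4 (used by 7.2) | Section 7.3.1 (first session) |
|---|---|---|---|
| Gavage at least 120 ml/kg/day | adequate feeding, no figure in this row | yes, criterion (2) | yes |
| At least 48 hours off CPAP | yes, before allocation | no | yes |
| PMA at least 28 weeks | no | no | yes |

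Only the feeding condition is required both for eligibility and for starting. The 48-hour condition precedes allocation in the overview but only precedes the first session in the body of the protocol.

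**2. How wide the gap is**

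- *Still on CPAP.* Criterion (4) would, on a natural reading, exclude most of these infants. Criterion (3) would too if it means already on high-flow support. Its wording can also be read as a forecast.
- *Off CPAP for less than 48 hours.* No criterion excludes these infants. This is the clear gap.
- *PMA below 28 weeks.* Criterion (1), "Preterm infants with a gestational age of less than 32+0 weeks", concerns birth and sets no minimum PMA. The floor matters only for infants born before 28 weeks who meet everything else before reaching it, probably few. For them the floor itself delays a start and does not prevent one.

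**3. What happens to an infant randomised in the gap who never starts**

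No session means not in ITT; not in ITT means not in FAS or PP. Section 9 does not clearly cover the case either: its respiratory rule concerns support beyond nasal positive pressure ventilation, so an infant who merely goes back on CPAP appears to meet no listed dropout criterion. Yet the primary outcome in section 8.3.1 runs from the start of oral feeding to full oral feeding and does not require a session, so it could still be recorded.

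**4. The plan's sample size, reproduced**

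Inputs from section 6.2: alpha 0.0167 two-sided, power 80%, means 20.8, 14.6 and 10.0 days, SD 7.19, dropout 10%.

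- Smallest contrast: 14.6 − 10.0 = 4.6 days.
- Two-sample t-test (noncentral t): 53 per group.
- Mann-Whitney allowance: 53 × π/3 = 55.5, rounded up to 56. This matches the plan. Section 6.2 does not name the test used for sizing; Mann-Whitney is listed in section 8.4.2.
- Dropout: 56 / 0.90 = 62.2, rounded up to 63; 63 × 3 = 189. This matches.

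**5. Effect of an assumed extra loss f**

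Evaluable infants per group: n = 63 × 0.90 × (1 − f). Noncentrality: 4.6 / (7.19 × √(2/n)). Power is from the two-sided t-test at 0.0167. The last column keeps 56 evaluable per group: 3 × 56 / (0.90 × (1 − f)), with the group size rounded up first.

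| f (assumed) | n per group | Noncentrality | Power | Total needed |
|---|---|---|---|---|
| 0% | 56.7 | 3.41 | 83.4% | 189 |
| 5% | 53.9 | 3.32 | 81.1% | 198 (66 × 3) |
| 10% | 51.0 | 3.23 | 78.6% | 210 (70 × 3) |

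The control versus DST contrast (20.8 − 14.6 = 6.2 days) needs only 30 per group by t-test and is little affected.

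**The case against.** The strongest reply is that the documents can be read together. Section 7.2 gives no time point, the overview supplies one, and the number is used at once to prescribe the intervention, which fits allocation at readiness. The web form also takes further data that are not listed, and these could include the start conditions. On that view the gap is a missing cross-reference. This reply narrows the point but does not remove it: eligibility in section 7.2 rests on criteria that lack both conditions, and nothing says that the form checks them.

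Three stronger readings are tempting.

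- *A reader might infer that infants still on CPAP would routinely be randomised.* Criterion (4) makes that unlikely for most of them.
- *A reader might infer that CPAP weaning would be steered by knowledge of the arm*, since section 5 calls the trial open-label. The overview also calls it blind, a screen and a matched control period are described, and no section says that the clinicians weaning CPAP learn the allocation. The coordinator does see the number, so the route is possible, but the documents do not establish it.
- *A reader might set 5% to 10% of 189 (9.45 to 18.9 infants) against the allowance of 189 − 168 = 21* and conclude that much of the allowance would be used up. That rate has no basis in the documents, and step 5 shows a modest effect on power.

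It is also fair to say that the loss from the analysis arises in section 8.4.1. Aligning the criteria would reduce the number of such infants; only a change to the analysis set deals with any who remain.

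**Conclusion.** The inconsistency stands and should be corrected. The overview places allocation after 48 hours off CPAP; sections 6.4 and 7.2 do not require this; section 7.3.1 requires it, with a PMA floor, only for the first session. The clear gap is mainly the first 48 hours after CPAP removal and, rarely, PMA below 28 weeks.

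The main consequence is exclusion after randomisation: an infant in the gap who never starts is in no analysis set, including the primary one. Power is secondary. On an assumed extra loss of 5% to 10%, added to the full 10% dropout, it falls by about 2 to 5 percentage points for the smallest contrast (83.4% to 81.1% or 78.6%). The true frequency cannot be derived from the documents and may be lower. The planned 56 per group, 168 and 189 are not called into question.

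**What to change.** 1. Reconcile the overview with sections 6.4, 7.2 and 7.3.1, so that randomisation takes place only when the start conditions that the sponsor confirms in section 7.3.1 are met. State in sections 6.4 and 7.2 that they are checked at randomisation.
2. Say whether inclusion criterion (3) describes an observed status at randomisation or a forecast.
3. Add these checks to the existing MRCC web form, so that a number is released only when all are confirmed.
4. In section 8.4.1, keep any randomised infant who does not start in the primary analysis set, in the group assigned.

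No clinical threshold or session schedule is proposed here; those stay with the sponsor.

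The cost is amendment wording and some extra fields on an existing form. The sample size does not change. The downside is that some infants whose guardians have consented will not be randomised.

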7.3.2. Frequency of implementation and the duration of each intervention

- DST group: The intervention will be administered once a day, for 15 minutes each session.
- DST + OSMS group: Both interventions will be applied once a day. DST will be administered once a day for 15 minutes, and OSMS will be performed once a day for 15 minutes as well. The order of the interventions is not specified, so they can be done in any sequence.
- Both groups will receive their respective interventions 5 times a week.

7.3.3 Discontinuation of intervention

The intervention will be discontinued when the infant can feed orally without requiring special treatment (including apnea, bradycardia, and oxygen desaturation) for two consecutive days during all feedings.

- If the infant is disrupted by factors such as taking sedatives or undergoing ophthalmologic exams

Protocol_DST and OSMS_oral feeding performance

within 30 minutes prior to the intervention, the intervention will not be applied that day.

- During the intervention, if any hemodynamic instability, apnea, bradycardia, or oxygen desaturation that does not resolve spontaneously occurs, the intervention will be stopped early. The intervention will only resume once the infant has stabilized and returned to a stable condition.

7.3.4. Detailed method for each intervention

Both the experimental group and the control group will continue the use of non-nutritive sucking through a rubber nipple and oral support during feeding, which are currently standard practices in the neonatal intensive care unit.

7.3.4.1. Direct swallowing training (DST)

The procedure will be carried out between feedings, lasting a total of 15 minutes.

Amount administered at one time: Formula milk (or distilled water if the caregiver refuses) is given at 1 ml. The administration starts with 0.05 ml using a syringe, gradually increasing by 0.05 ml increments while checking for the presence of a swallowing reflex. Once this threshold is determined, the procedure will continue using that dose. The maximum volume administered will not exceed 0.2 ml.

Administration site: The milk will be dropped onto the tongue at a level approximately where the soft palate and hard palate meet, specifically in the central-to-posterior region of the tongue.

Interval between administrations: The procedure will be performed at 30-second intervals for a total of 15 minutes.

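### Section 7.3.4.1 sets the single DST amount at 1 ml, five times the 0.2 ml maximum in the same paragraph, and 1 ml does not fit as a session total either

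*Combined protocol and SAP*

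**What the plan says.** The volume of DST is given in one paragraph of section 7.3.4.1. It opens with "Amount administered at one time: Formula milk (or distilled water if the caregiver refuses) is given at 1 ml". It goes on: "The administration starts with 0.05 ml using a syringe, gradually increasing by 0.05 ml increments while checking for the presence of a swallowing reflex". Then: "Once this threshold is determined, the procedure will continue using that dose". It closes with "The maximum volume administered will not exceed 0.2 ml". The timing follows in the same section: "The procedure will be performed at 30-second intervals for a total of 15 minutes".

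Section 7.3.2 sets one session a day. For the DST group it says "The intervention will be administered once a day, for 15 minutes each session", and for the combined group "DST will be administered once a day for 15 minutes". No other section gives a DST volume or explains the 1 ml.

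**The concern.** The opening sentence and the closing limit both appear to describe the amount given each time, yet they differ by a factor of five. The obvious rescue is to take the 1 ml as the amount for the whole session, but the paragraph's own steps and schedule do not allow that.

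Three things are at stake.

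- **Safety.** The liquid is placed on the central to posterior tongue of preterm infants. Under section 7.3.1 they may start from 28 weeks' postmenstrual age, while receiving full gavage feeds. Section 7.3.3 says when to interrupt a session after an event, but not which volume applies.
- **Treatment definition.** DST is given in both active arms, and each of the three primary hypotheses in section 6.2 involves at least one of them.
- **Adherence.** The per-protocol set in section 8.4.1 depends on strict adherence to the protocol. Adherence on volume cannot be judged against figures that conflict.

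**Working it through.** **Inputs**

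- Amount under the single-administration label: 1 ml (7.3.4.1)
- Start and step: 0.05 ml each (7.3.4.1)
- Stated maximum: 0.2 ml (7.3.4.1)
- Interval and session length: 30 seconds, 15 minutes (7.3.4.1)
- Sessions per day: one (7.3.2)
- Planned infants: 189, allocated 1:1:1 (6.2)

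The protocol gives no derivation of the 1 ml, so there is no calculation to reproduce. Each possible meaning is tested against the other figures.

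**1. Amount per administration (as labelled).** 1 / 0.2 = 5 times the maximum, and 1 / 0.05 = 20 times the start. Given at every interval, it would come to 30 × 1 = 30 ml a session.

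**2. Session total.** Number of administrations = 15 min / 30 s = 30 (29 or 31, depending on whether the end points are counted). Taking 0.2 ml as a limit per administration:

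| Volume each time | 29 | 30 | 31 |
|---|---|---|---|
| 0.05 ml | 1.45 ml | 1.5 ml | 1.55 ml |
| 0.10 ml | 2.9 ml | 3.0 ml | 3.1 ml |
| 0.15 ml | 4.35 ml | 4.5 ml | 4.65 ml |
| 0.20 ml | 5.8 ml | 6.0 ml | 6.2 ml |

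If each session steps up from the start with one administration per step (an assumption), the 30-administration total at the 0.2 ml threshold is 0.05 + 0.10 + 0.15 + 27 × 0.20 = 5.70 ml.

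The smallest total for a completed session is therefore 1.45 to 1.55 ml, above 1 ml under every counting convention. Conversely, 1 ml spread over 30 administrations is 1 / 30 = 0.033 ml each, below the 0.05 ml first step. At 0.05 ml, 1 ml is used up after 1 / 0.05 = 20 administrations (10 minutes). At 0.2 ml, it is used up after 1 / 0.2 = 5 (2.5 minutes).

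The four-fold spread from 1.5 to 6.0 ml comes from the planned individual titration and is not an error.

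**3. Daily total.** With one session a day, this is the same as reading 2.

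**4. The 0.2 ml read as a session cap instead.** Then 0.2 / 0.05 = 4 administrations at the lowest volume would reach it, so it would conflict with both the 1 ml and the 15-minute schedule.

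**5. Quantity drawn up in the syringe.** A 1.5 ml session needs 2 fills of 1 ml and a 6.0 ml session needs 6. This is compatible with the other figures, but it is not what the sentence says.

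**Reach of the paragraph.** 189 / 3 = 63 per arm, and 2 × 63 = 126 infants are planned for the two DST arms. This is the number governed by the paragraph, not an estimate of how many would receive a different volume.

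**The case against.** The strongest reply is that the 1 ml sentence does not stand alone. The next three sentences give a starting volume, a step, a rule for when to stop stepping and an explicit limit. An operator would have to disregard that limit to give 1 ml at once, so the 5-fold and 30 ml figures describe a delivery that the paragraph itself forbids. Since a drawn-up quantity would fit the other figures, the fault may be an undefined term or a translation slip rather than a real conflict over dose. The interruption rules in section 7.3.3 add a safeguard.

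Much of this is fair. Nothing in the documents shows that any infant received 1 ml at once, and the ratios measure how far the sentences clash, not how likely the exposure is. The session totals also depend on reading 0.2 ml as a limit per administration. That is the natural reading under the shared label, though it is not spelled out.

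The reply does not remove the conflict. The sentence states an amount given, not a quantity prepared, and nothing elsewhere assigns it another meaning. That a compatible but unwritten meaning exists is a reason to write it down. The interruption rules act after an event and do not settle the volume.

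**Conclusion.** The concern holds. As labelled, 1 ml is five times the maximum stated in the same paragraph. As a total for a completed session or day, it lies below the smallest volume the schedule can deliver (1.5 ml, or 1.45 to 1.55 ml depending on the count). The five-fold ratio assumes that the 0.2 ml limit applies to each administration; if it were a session cap, the figures would still conflict. The session comparison assumes a completed 15-minute session, since one stopped early could deliver 1 ml or less.

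The documents do not show which figure is intended, and this review takes no position on that. The conflict concerns the volume of the experimental treatment in both active arms, so it needs correcting even though the statistical design is unaffected.

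**What to change.** The sponsor should reconcile the 1 ml figure in section 7.3.4.1 with the 0.05 to 0.2 ml steps and the 30-second, 15-minute schedule. The revised paragraph should state what the 1 ml refers to. It should also label each volume, including the 0.2 ml maximum, as per administration or per session, so that volume times number of administrations gives the stated total. The clinical team chooses the figures.

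The cost is the wording of one paragraph, with no extra patients, visits or data.

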7.3.4.2. Oral sensorimotor stimulation (OSMS)

The procedure will be carried out 15-30 minutes before the tube feeding, specifically during behavioral stages 3-5, and the total duration will be 15 minutes.

Composition	stimulation	Objective	Duration	
Trigging sucking reflex	Cheek	1) Place the index finger on the philtrum (the area above the upper lip). 2) Gently press and apply pressure, moving towards the ear and then back to the corner of the mouth, tracing a "C" shape.	Enhance the range of motion and strength of the cheeks, and improve lip closure.	4 min.

Protocol_DST and OSMS_oral feeding performance

Curling and pulling the upper and lower lips	1) Place the index finger at the center of the upper lip. 2) Continue pressing and pull downward, rolling the lip. 3) Place the index finger at the center of the lower lip, press, and pull upward, rolling the lip.	Enhance lip strength, range of motion, and lip closure.	30 sec
Upper lip	1) Place your index finger on one side of the upper lip. 2) Gently press down. 3) Move your finger in a circular motion, starting from one end, passing through the center of the lips, and ending at the opposite side.	Improvement of lip range of motion and lip closure strength.	30 sec
Lower lip	1) Place your index finger on one corner of the lower lip. 2) Gently press down. 3) Move in a circular motion, starting from one corner, passing through the center of the lip, and continuing to the opposite corner.	Improvement of lip range of motion and lip closure strength.	30 sec
Inside of the cheek	1) Place your finger on the inside of the corner of the mouth. 2) Gently press and move towards the molars, then return to the corner of the mouth.	Improvement of the range of motion of the cheeks and lip closure.	1 min
Upper gums	1) Place your finger on the center of the upper gums and press firmly, slowly moving inward inside the mouth.	Range of tongue motion, swallowing stimulation, and	40 sec

Protocol_DST and OSMS_oral feeding performance

	2) Slowly return to the center.	sucking improvement.	
Lower gums	1) Press your finger firmly on the center of the lower gum and slowly move it inward. 2) Slowly return to the center.	Range of tongue motion, swallowing stimulation, and sucking improvement.	40 sec
Side of the tongue	1) Place your finger between the side of the tongue and the gum near the molars. 2) Move your finger toward the center while pushing the tongue in the opposite direction. 3) After pushing the tongue, immediately return to the cheek and stretch it as much as possible.	Tongue range of motion and strength enhancement	30 sec
Dorsal surface of the tongue	1) Place the index finger in the center of the mouth. 2) Press against the hard palate for 3 seconds. 3) Place your finger on the center of the tongue and press down firmly. 4) Immediately return to the center of the hard palate after pressing the tongue.	Tongue range of motion and strength enhancement, swallowing stimulation, sucking improvement	40 sec
Induce sucking	1) Place your finger in the center of the palate and gently rub it to induce sucking.	Sucking improvement, velum activation	3 min
Pacifier	1) Place the pacifier in the mouth and gently move it in a rhythmic motion, up/down and front/back.	Sucking improvement, velum activation	3 min.

